7.6.4. Lost to Follow-up

If attempts to contact a subject by telephone are unsuccessful, additional attempts should be made during the study to complete study-related assessments and record outstanding data. It may be possible to obtain the information from other contacts, such as referring physicians or primary care providers.

Attempts to contact should be documented in the subject's source documents. If a subject cannot be contacted despite all attempts, the subject will be considered lost to follow-up.

7.7. Premature Discontinuation From Study Treatment or From the Study

7.7.1. Subject Premature Discontinuation From the Study Treatment

Eligible subjects will receive the administration of study drug(s) and they have the right to discontinue the study drug(s) at any time for any reason during the study treatment. In addition, the investigator has the right to discontinue a subject from the study drug(s) at any time during the study treatment. Subjects who discontinue the study treatment should follow the procedures and the assessments specified in EOS Visit (Section 7.6.2). Subjects who could not complete the infusion or did not receive any study drug after the randomization should be replaced.

The primary reason for discontinuation from the study treatment should be documented on the appropriate eCRF. Subjects may discontinue from the study treatment for reasons that include, but are not limited to, the following:

- Withdrawal of consent
- The investigator or sponsor determines it is in the best interest of the subject
- Significant or persistent AE(s) as described in Section 9.8.

7.7.2. Subject Premature Discontinuation From the Study

Subjects may discontinue from the study for reasons that include, but are not limited to, the following:

- Subject withdrawal of consent
- Study termination by sponsor
- Lost to follow-up
- Positive for COVID-19

Subjects may voluntarily withdraw consent from the study at any time. A subject who discontinues from the study before Day 29 may be replaced.

7.8. End of Study

The end of study is defined as the timepoint when the final data for a clinical study were collected, which is after the last subject has made the final visit to the study center.

Alternatively, the end of study is when the sponsor decides to terminate the study. The sponsor has the right to terminate this study at any time. Reasons for terminating the study early include, but are not limited to, the following:

- The incidence or severity of AEs in this or other studies on BGB-DXP604 or BGB-DXP593 indicates a potential health hazard to subjects
- Overall subject enrollment is unsatisfactory

The sponsor will notify the investigator if a decision is made to terminate the study. Should this be necessary, prematurely discontinued subjects must be seen for an EOS Visit as described in Section [7.6.2](#).

The investigators may be informed of additional procedures to be followed to ensure that adequate consideration is given to the protection of the subject's interests. The investigator will be responsible for informing IRBs/IECs of the early termination of the study.

8. STUDY ASSESSMENTS

A table of scheduled study assessments is provided in [Appendix 1](#). Subjects will be closely monitored for safety and tolerability throughout the study. All assessments will be performed on the day of the specified visit and documented in the medical record for each subject.

Where applicable, the study drug(s) will be administered only if the clinical assessment and laboratory test values have been reviewed and found to be acceptable per protocol guidelines.

8.1. Screening Assessments

Screening evaluations will be performed within 28 days before receiving the study drug(s). The screening period begins when the ICFs were signed by the subjects. The investigator will assess subject eligibility according to the latest screening assessment results.

8.1.1. Demographic Data, Medical History, and Prior Medications

Demographic data will include age or year of birth, gender, and race/ethnicity.

Medical history includes any history of clinically significant disease, surgery history, reproductive status (ie, no childbearing potential or childbearing potential), and smoking history.

Prior medications include all medications (eg, prescription drugs, over-the-counter drugs, herbal medications) used by the subject within 28 days before administration of study drug(s).

8.2. Safety Assessments

8.2.1. Vital Signs

Vital signs will include measurements of body temperature (°C), pulse rate, respiratory rate, and blood pressure (systolic and diastolic). Pulse rate and blood pressure will be measured while the subject is in a supine position after resting for 10 minutes.

Height and weight will be measured at screening and weight will be measured again on Day -1. The data of height and weight will be recorded in the eCRF.

8.2.2. Physical Examinations

During the Screening Visit, a complete physical examination will be conducted, including evaluations of 1) head, eyes, ears, nose, and throat, 2) cardiovascular, 3) dermatological, 4) musculoskeletal, 5) respiratory, 6) gastrointestinal, and 7) neurological systems. Any abnormality identified during screening will be graded according to NCI-CTCAE v5.0 and recorded in the eCRF with appropriate disease/condition terms.

At subsequent visits (and as clinically indicated), limited, symptom-directed physical examinations will be performed. New or worsened clinically significant abnormalities are to be recorded as AEs in the eCRF. Refer to Section [9.4](#) regarding AE definitions and reporting and follow-up requirements.

8.2.3. Laboratory Safety Tests

Samples for protocol-specified clinical chemistry, hematology, urinalysis, and coagulation profiles will be evaluated by a local laboratory.

A pregnancy test will be performed for female subjects of childbearing potential during the study. Samples for pregnancy testing will also be assessed locally. The urine pregnancy test will be performed at the Screening Visit, and the next urine pregnancy test will be conducted after the admission on Day -1 and before administration of study drug(s) on Day 1. Female subjects of childbearing potential with negative results will be eligible to receive the study drug(s). Afterwards, urine pregnancy test will be performed. A serum pregnancy test must be performed if the urine pregnancy test is positive or equivocal.

See [Appendix 4](#) for the list of clinical laboratory tests to be performed and [Appendix 1](#) for the timing and frequency. Additional tests may be performed at any time during the study as deemed necessary by the investigator or as required by local regulations. If required by local regulations, clinical laboratory evaluations performed by a local (instead of a central) laboratory are acceptable.

A detailed description of the procedures for sample collection, handling, storage, and shipment of the laboratory samples and all materials such as test tubes and labels are provided in the Laboratory Manual.

8.2.4. Electrocardiograms

For safety monitoring purposes, the investigator must review, sign, and date all ECG tracings. Paper or electronic copies of ECG tracings (per local practice) will be kept as part of the subject's permanent study file at the site.

The subject should rest in a semirecumbent or supine position for ≥ 10 minutes in the absence of environmental distractions that may induce changes in heart rate (eg, television, radio, conversation) before each ECG collection.

At each timepoint (see [Appendix 1](#)), 3 consecutive 12-lead ECGs will be performed approximately 2 minutes apart and within a maximum of 10 minutes to calculate heart rate and measure QT and QTcF intervals.

8.2.5. Cardiac Telemetry

The cardiac telemetry will be performed from approximately 1 hour predose to 24 hours post dosing. The full disclosures will be maintained electronically by the site as part of the subject's source documents.

8.2.6. Adverse Events

AEs will be graded and recorded throughout the study according to NCI-CTCAE v5.0. Characterization of toxicities will include severity, duration, and time to onset.

All AEs, including SAEs, will be collected as described in Section [9.7](#).

8.2.7. Serology

The testing of HBV/HCV serology (HBsAg, HBcAb, and HCV antibody) will be performed at screening. In the case of positive HCV antibody, the test of HCV RNA will be followed.

Blood from all subjects will be collected and tested for HIV antibody at screening. Those subjects with negative results can be enrolled.

Specific IgG antibodies against SARS-CoV-2 in the serum of all subjects will be measured by quantitative or qualitative antibody testing. Those subjects with negative results can be enrolled.

The tests mentioned above will be performed at a local laboratory.

8.2.8. Virology

The nasopharyngeal or oropharyngeal swab will be collected during the screening and at the visit on Day 29. The nasopharyngeal or oropharyngeal swab will be tested by the method of rRT-PCR in a local laboratory for the qualitative detection of nucleic acid from SARS-CoV-2 in upper respiratory specimens. During the screening, those subjects who have negative results can be enrolled.

If any subject has positive or suspected result during the study, the subject will be discontinued from the study and treated by following local practice. If the subject is unable to complete the EOS Visit, please see the procedures in Section 7.6.2 and Section 7.6.4.

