1.5. Benefit-Risk Assessment

This is a FIH study for BGB-DXP604 and the side effects of BGB-DXP604 in humans are unknown.

The healthy subjects in this study will not receive any health benefit from participating in the study other than an assessment of their medical status.

The subjects might have some discomfort from blood collection and other study procedures. Other than that, the risks of study participation include possible adverse reactions associated with BGB-DXP604, such as infusion-related reactions. However, because BGB-DXP604 is a human protein selected from recovered COVID-19 patients, it is unlikely to have any pharmacodynamic effect in healthy subjects. Therefore, the risks are generally low under the current safety monitoring planned for this study.

As exogenous proteins, BGB-DXP604 used alone or in combination with BGB-DXP593 might lead to hypersensitivity reactions, although immunogenicity is considered low due to its human origin. Potential antibody dependent enhancement (ADE) has been observed in some viral infections, such as dengue fever. The possibility of ADE with passive immunity cannot be excluded in COVID-19. However, clinical experiences with respiratory syncytial virus, influenza, and dengue provide strong evidence that the circumstances thought to lead to ADE of disease—including low affinity or cross-reactive antibodies with limited or no neutralizing activity or suboptimal titres—are very rarely implicated as the cause of severe viral infection in the human host (Arvin et al 2020). BGB-DXP604 and BGB-DXP593 are highly potent neutralizing antibodies, and thus are unlikely to cause ADE. In addition, a large number of COVID-19 patients have received convalescent plasma therapy, where no hints of ADE have been identified (Joyner et al 2020).

To further minimize the risk to the subjects, the method of sentinel dosing will be adopted for this study and each healthy subject in the study will receive only a single dose of study drug(s).

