4.1. Inclusion Criteria

Each subject must meet all the following inclusion criteria to be considered eligible for participation in this study:

1. Male and female subjects 18 to 60 years of age, inclusive, at the time of signing the informed consent
2. Subjects are in good general health as determined by the investigator or medically qualified designee, based on a medical evaluation including medical history, physical examination, laboratory tests, and cardiac monitoring
3. Body weight ≥ 50 kg and body mass index (BMI) within the range 18 to 32 kg/m² (inclusive)

Note: BMI = weight [kg] / (height [m])²

4. Negative SARS-CoV-2 serology test
5. Negative for COVID-19 based on the nasopharyngeal or oropharyngeal swab with the method of real-time reverse transcription-polymerase chain reaction (rRT-PCR)
6. Female subjects of childbearing potential must be willing to use a highly effective method of birth control (see [Appendix 5](#)) from the time of study enrollment until 4 months after the single dose of study drug(s)
7. Male subjects with female partners of childbearing potential must be willing to use a highly effective method of birth control (see [Appendix 5](#)) from the time of study enrollment until 4 months after the single dose of study drug(s)
8. Able to provide written informed consent and can understand and agree to comply with the requirements of the study and the schedule of assessments.

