7.1. Screening Period

Screening evaluation will be performed within 28 days before administration of study drug(s). A subject who agrees to participate in this study will sign the informed consent form (ICF) before undergoing any study-specific procedures. Refer to Section [8.1](#) for instructions regarding screening assessments.

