7.3. Check-in (Day -1)

The enrolled subjects will be admitted ≥ 12 hours before the administration of study drug(s). On the day of admission, screening for alcohol/drugs, a review of the inclusion/exclusion criteria, laboratory assessments of hematology, clinical chemistry, coagulation, urinalysis, and safety assessments of vital signs and weight will be performed. Smoking will be not allowed during the inpatient stay.

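### The qualifying SARS-CoV-2 swab may be up to 28 days old at dosing and is not repeated at admission, so a subject with a silent infection can be dosed

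*Protocol*

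**What the plan says.** Protocol Section 4.1 has two SARS-CoV-2 entry criteria. Inclusion 4 is "Negative SARS-CoV-2 serology test". Inclusion 5 is "Negative for COVID-19 based on the nasopharyngeal or oropharyngeal swab", by rRT-PCR. Neither states how recent the result must be.

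Sections 7.1 and 8.1 allow screening evaluations up to 28 days before dosing, and the screening column of Appendix 1 runs from Day -28 to Day -1. Section 8.2.8 fixes the swab times: "The nasopharyngeal or oropharyngeal swab will be collected during the screening and at the visit on Day 29". Appendix 1 has no swab in the Day -1 or Day 1 column.

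At check-in (Section 7.3) the subject has an alcohol/drug screen and a review of the eligibility criteria, and "laboratory assessments of hematology, clinical chemistry, coagulation, urinalysis, and safety assessments of vital signs and weight will be performed". Section 8.2.3 adds a second urine pregnancy test between admission and dosing. Exclusion 6 (Section 4.2) keeps out anyone with an acute febrile illness or infection. No isolation between screening and admission is described.

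**The concern.** At admission the plan rechecks several states that can change during a four-week screening window: blood and urine results, alcohol and drug use, and pregnancy. Acute SARS-CoV-2 infection can also change in that time and is not rechecked, although it is the disease the antibodies target. The eligibility review on Day -1 therefore relies on whatever swab is on file.

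The main stake is attribution. This is a first-in-human study with 6 active and 2 placebo subjects per cohort. Under Protocol Section 10.3.2 and SAP Section 6.5.2, any adverse event starting from dosing to 30 days afterwards is a TEAE, whatever its cause. Symptoms of an infection already present at dosing would enter the primary endpoint. They could fall within the 48-hour sentinel period or the follow-up of at least 5 days before Safety Monitoring Committee (SMC) review. A positive or suspected result also leads to discontinuation from the study (Sections 7.7.2 and 8.2.8), which cuts short PK and ADA follow-up planned to Day 113.

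Subject safety is involved too. Section 1.5 says of antibody-dependent enhancement (ADE) that "The possibility of ADE with passive immunity cannot be excluded in COVID-19", although it goes on to call ADE unlikely with these antibodies.

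**Working it through.** The plan states no figure to reproduce; the sample size is explicitly not statistical (Protocol Section 10.6, SAP Section 5). The check is of the schedule, followed by simple arithmetic.

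**1. What is rechecked between screening and dosing**

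| State | Screening | Day -1, or before dosing |
|---|---|---|
| Hematology, chemistry, coagulation, urinalysis | yes | yes |
| Alcohol/drug screen | yes | yes |
| Pregnancy test | yes | yes |
| Vital signs, including temperature | yes | yes |
| SARS-CoV-2 rRT-PCR swab | yes | no |

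**2. Intervals.** SAP Section 6.2.1 states that there is no study day 0.
- Day -28 to Day 1: 28 days at most.
- Day 1 to Day 29: 29 − 1 = 28 days.
- Between the two scheduled swabs: 28 + 28 = 56 days at most, or 57 with the +1-day window at Day 29 (Section 8.4).

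Dosing lies between the two swabs, so a positive Day 29 result does not show whether infection came before or after it. Appendix 1 schedules the IgG test at screening only. A later IgG test might not settle the order, because BGB-DXP604 is itself an IgG1 that binds the viral receptor-binding domain (Sections 1.2 and 1.2.1.1) and the assay's target is not stated.

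**3. Weight of one subject.** Planned N = 3 × (6 + 2) = 24, of whom 3 × 6 = 18 are active. One affected subject is 1/6 = 16.7% of a cohort's active arm, or 1/18 = 5.6% of all active subjects.

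**4. Illustrative probability.** Let p be the risk of infection over the four weeks between swab and dosing. The documents give no value; 0.1% to 1% is assumed. P(at least one of n) = 1 − (1 − p)^n.

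| Case | p = 0.1% | p = 1% |
|---|---|---|
| All 24 planned subjects | 1 − 0.999^24 = 2.4% | 1 − 0.99^24 = 21.4% |
| 18 active subjects only | 1 − 0.999^18 = 1.8% | 1 − 0.99^18 = 16.5% |
| 24 subjects, swab 14 days before dosing on average | 1 − 0.999^12 = 1.2% | 1 − 0.99^12 = 11.4% |
| 24 subjects, swab 3 days before dosing | 1 − 0.999^(24 × 3/28) = 0.26% | 1 − 0.99^(24 × 3/28) = 2.6% |

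The last two rows assume a constant daily risk. The first two are upper bounds for the assumed p: every subject is swabbed on Day -28, nobody is caught clinically on Day -1, and any infection in the 28 days still matters at dosing.

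**The case against.** The strongest reply is that the window is permissive, not contradictory. A swab on Day -2 already complies, Section 8.1 bases eligibility on the latest screening results, and 28 days is only the extreme. There are also real safeguards. Exclusion 6, temperature and a white-cell differential on Day -1 can reveal an overt infection. Section 9.4.3 has the investigator consider alternative causes for every event. Section 8.5 allows diagnostic tests at unscheduled visits, so a subject who becomes ill after dosing can be swabbed. All of this stands. It narrows the gap to infections without signs at check-in but does not close it, because nothing in the text requires a recent swab.

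A reader might infer more than the documents support:
- **That a cohort would be halted.** Section 3.4 requires a related serious or Grade 4 or higher event, or related Grade 3 events in at least 2 subjects. The investigator would have to attribute the infection to the drug, and even then the SMC may continue enrollment as planned.
- **That ADE is an expected harm.** Section 1.5 leaves it open but describes the relevant circumstances as very rarely implicated, and Section 1.1 describes a planned study of the companion antibody in patients with COVID-19.
- **That a dosed, infected subject would spread infection in the unit.** This depends on site procedures and local incidence, which the documents do not give.
- **That the single IgG test is also a fault.** The point rests on the swab alone, and the fix leaves serology unchanged.

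**Conclusion.** The point holds as a gap in the timing of an eligibility test. The protocol allows a qualifying swab up to 28 days old, with no recheck at admission, so a subject with presymptomatic or asymptomatic infection can be dosed within the rules. If that happens, one subject shifts a cohort's active-arm TEAE incidence by up to 16.7 percentage points. Two placebo subjects per cohort (6 pooled) give little help in separating infection from drug effects.

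How likely this is cannot be derived from the documents. The 2.4% to 21.4% range is an assumed upper bound, not an estimate, and the true figure could be lower still. No hypothesis is tested, so no power or error rate is affected. This is a cheap improvement to safety and attribution, not a flaw that invalidates the study.

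**What to change.** In Inclusion 5, Sections 7.3 and 8.2.8 and Appendix 1, require the existing eligibility swab to be taken within a short stated interval before dosing, with the result available before randomization. An interval of 72 hours is an example, not a figure derived from the documents; the sponsor should choose one that the local laboratory's turnaround can meet. It fits the present Day -28 to Day -1 window and the present timing of randomization (after admission on Day -1, before dosing on Day 1).

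Moving the swab adds no test. Keeping the early swab and adding one at check-in would also close the gap, at one local rRT-PCR per subject. In either case some subjects will fail screening late, so standby subjects are needed for each dosing day.

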8.3. Pharmacokinetic Assessment and Antidrug Antibody Testing

Blood will be collected to characterize the PK profile of BGB-DXP604 or BGB-DXP593 using validated immunoassays. Blood samples will be collected for characterization of anti-BGB-DXP604 or anti-BGB-DXP593 antibodies. Validated screening and confirmatory assays will be employed to detect ADAs in the samples. Samples collected for analyses of blood concentration may also be used to evaluate safety or efficacy aspects related to concerns arising during or after the study.

Blood sampling for PK and ADA will be collected at the timepoints specified in the PK and immunogenicity sampling schedule ([Appendix 3](#)).

The PK and ADA assays for BGB-DXP604 or BGB-DXP593 will be managed through a central laboratory. Refer to the laboratory manual for instructions regarding sample collection, handling, labeling, storage, and shipping of laboratory samples. The actual time of each sample collected will be captured to the nearest minute in the eCRF and recorded in the database.

8.4. Visit Windows

The PK sampling schedule allows for a visit window of ± 1 day for the visits at Day 15, Day 22, and Day 29, and a visit window of ± 2 days for the visits at Day 43, Day 57, Day 71, Day 85, and Day 113 ([Appendix 1](#) and [Appendix 3](#)). All assessments will be performed on the day of the specified visit.

8.5. **Unscheduled Visits**

Unscheduled visits may be performed at any time at the subject's or investigator's request if there are any safety concerns. The date and reason for the unscheduled visit must be recorded in the source documentation.

If an unscheduled visit is necessary to assess toxicity, then diagnostic tests may be performed based on the investigator's assessment as appropriate, and the results of these tests should be recorded on the unscheduled visit eCRF.

9. SAFETY MONITORING AND REPORTING

The investigator is responsible for the monitoring and documentation of events that meet the criteria and definition of an AE or SAE as provided in this protocol.

9.1. Risks Associated With BGB-DXP604

This is the FIH study of BGB-DXP604. No clinical data are available yet and no risk associated with BGB-DXP604 has been identified. In the 18-day repeat-dose toxicology study, no apparent toxicity was observed in cynomolgus monkeys at doses of 30 mg/kg, 100 mg/kg, or 300 mg/kg once every week for 3 doses.

